# 7. Study population

The annual number of deliveries per NHS Trust in England ranged from 3,000 to 13,000 in the year 2022 to 20239. NICE guidance recommends that all newborn babies are examined for jaundice at every opportunity, especially in the first 72 hours5. If jaundice is suspected, a bilirubin level should be measured. This is primarily done by midwives either in the community or in a secondary care setting. While exact guidelines vary within secondary care settings, TcB is commonly used in neonates over 24 hours of age who visibly appear jaundiced or meet a risk factor for jaundice1. TcB measurements within a certain threshold of the phototherapy treatment line should then undergo SBR testing5. As jaundice affects approximately

60% of term newborn babies, sufficient numbers of patients are expected to meet study inclusion criteria during a short timeframe.

#### 7.1. Inclusion criteria

Participants will be recruited for the Primary Objectives (quantitative) data collection if they fulfil the following criteria:

- 1. Neonates born at ≥ 34 weeks gestation, now between 0-14 days postnatal age
- 2. Inpatients on any ward providing postnatal care excluding the neonatal unit or paediatric ward
- 3. Undergoing first objective assessment of bilirubin level for any reason (i.e. targeted screening, suspected jaundice by healthcare professional, suspected jaundice by parent / carer, poor feeding, any other clinical indication)
- 4. Age of parent/ carer ≥18 years

Participants will be recruited for Secondary Objective 3 (qualitative) data collection (survey and / or focus groups / semi-structured interviews) if they fulfil the following criteria:

- 1. Parent or carer of neonate eligible for inclusion into the quantitative data collection section of study (even if they have opted out of quantitative data collection).
- 2.  $\geq$ 18 years of age.

#### 7.2. Exclusion criteria

Exclusion criteria for the Primary Objectives (quantitative) data collection:

- 1. Readmission from the community
- 2. Parent/carer opted out of consent for the study
- 3. Any medical condition known to affect skin colour e.g. cyanotic heart disease or widespread skin condition
- 4. Enrollment in a competing and/or overlapping study or trial anticipated to alter in any way data collected in this study

Exclusion criteria for Secondary Objective 3 (qualitative) data collection (survey and / or focus groups / semi-structured interviews):

1. Has not provided consent for participation in the respective section (survey or group).

## 7.3. Vulnerable participant considerations

The PI is responsible for ensuring that all vulnerable participants are protected and participate voluntarily in an environment free from coercion or undue influence. This study is low risk with minimal deviation from standard care. Participation is based on an opt-out consent model with no change to standard clinical care for patients who do not participate. If a GCP-trained individual providing the explanation of the study

has concerns about the capacity of the parent or carer to understand the study, the participant will not be enrolled.

# 8. Study design

This is a prospective multicentre observational study utilising the London REACH (Research Evaluation and Audit for Child Health) Network. It will investigate detection of jaundice in neonates of different skin tones, in a clinically relevant population.

The REACH Network has a successful track record in running high quality, multi-site studies with significant outputs with trainee and consultant leads in 26 London Hospitals where routine postnatal care is provided. This study will aim to recruit patients in the majority of these, which may include:

- Whipps Cross Hospital (Barts Health NHS Trust)
- Newham Hospital (Barts Health NHS Trust)
- Royal London Hospital (Barts Health NHS Trust)
- Queen's Hospital (Barking, Havering and Redbridge University Hospitals NHS Trust)
- North Middlesex University Hospital (North Middlesex University Hospital NHS Trust)
- Homerton University Hospital (Homerton University Hospital NHS Foundation Trust)
- Royal Free Hospital (Royal Free London NHS Foundation Trust)
- Barnet General Hospital (Royal Free London NHS Foundation Trust)
- University College London Hospital (University College London Hospitals NHS Foundation Trust)
- Whittington Hospital (Whittington Health NHS Trust)
- Chelsea and Westminster Hospital (Chelsea and Westminster Hospital NHS Foundation Trust)
- West Middlesex Hospital (Chelsea and Westminster Hospital NHS Foundation Trust)
- St Mary's Hospital (Imperial College Healthcare NHS Trust)
- Norwick Park Hospital (London North West University Healthcare NHS Trust)
- Queen Charlotte's and Chelsea Hospital (Imperial College Healthcare NHS Trust)
- Hillingdon Hospital (The Hillingdon Hospitals NHS Foundation Trust)
- Evelina Children's Hospital (Guy's and St Thomas' NHS Foundation Trust)
- St George's Hospital (St George's University Hospitals NHS Foundation Trust)
- Kings College Hospital (King's College Hospital NHS Foundation Trust)
- Princess Royal University Hospital (King's College Hospital NHS Foundation Trust)
- Kingston Hospital (Kingston Hospital NHS Foundation Trust)
- Lewisham University Hospital (Lewisham and Greenwich NHS Trust)
- Queen Elizabeth Hospital Woolwich (Lewisham and Greenwich NHS Trust)
- Croydon University Hospital (Croydon Health Services NHS Trust)
- Queen Mary's Hospital for Children, St Helier Hospital (Epsom and St Helier University Hospitals NHS Trust)
- Epsom General Hospital (Epsom and St Helier University Hospitals NHS Trust)

Following initial sample size calculations (detailed in Section 10) it has been estimated that a total of 560 participants will need to be recruited, to adequately power the study's Primary Objectives 1 and 2. Therefore, we will aim to recruit a

minimum of 28 participants at each site. An initial recruitment window will aim to recruit 10 participants per site. If there is insufficient recruitment to particular skin tone groups, recruitment windows can be reopened in centres where recruitment of participants of that group is most likely.

Data collection periods may need to be staggered according to the timings of individual Trust R&D approval processes. The total anticipated time for the study is currently 18 months, of which approximately the first 9 months will include local site approval processes and data collection, followed by a 9 month period of analysis and preparation for dissemination (see Gantt chart attached for further detail).

#### Study processes during prospective data collection phase

Potentially eligible neonates will be identified by postnatal area healthcare professionals and REACH/BiliNEST local study team members will determine their eligibility. The research team at each site will consist of the local lead study team member and a number of additional data collectors who have undergone training, all of whom are paediatric resident doctors as part of the direct care team. These individuals will review whether or not these neonates meet the eligibility criteria, and approach the birthing parent to ask if they are happy to discuss a research study. The number of participants deemed ineligible and the reason for exclusion will be documented. The study process and opt-out consent model will be explained verbally, and patient information leaflets will be provided in English or in the most relevant language available.

Local data collectors will receive an SOP detailing the introductory conversation aims with parents / carers, in particular, to be clear that there will be no detrimental consequences to them or their child if they opt out. A filmed, scripted example of an introduction will be included, that uses sensitive, non-coercive language; the script of which has been vetted by our PPI group. In addition, all data collectors will have completed Good Clinical Practice training, which includes the principles of appropriately obtaining informed consent and will have attended a training session on study processes.

The data collected from the parent/carer is listed in Table 1. The only data collected from participant examination is skin tone / colour group. Neonates will undergo a visual inspection by local study team members within twelve hours of their first bilirubin measurement and then categorisation into one of the four skin colour groups. We recognise that babies may be naturally lighter or darker than those depicted in the skin tone tool groups. When this is the case, babies will be assigned to the group closest to their natural skin colour e.g. for a baby who has a skin colour darker than group 4, they will be included within group 4. All study team members will be trained in the use of the tool to ensure the use of acceptable language and to minimise inter-user variability.

During quantitative data collection periods, all eligible neonates undergoing assessment for jaundice will be considered for inclusion, as identified by postnatal area staff. Parents will be approached and given verbal and written (PIS) information about the study. If, after further consideration, the participant meets all inclusion

criteria and no exclusion criteria, and parents do not object, they will be enrolled to participate.

Within the PIS there will be links for the parents and carers to additionally consent for inclusion in the qualitative sections of the study. These will also be verbally explained at the time of enrollment above, and an opportunity given for questions. If participants meet inclusion criteria and no exclusion criteria, they will be enrolled into these sections respectively.

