Our preliminary survey has also helped ensure that language used in the PIS is clear and easily understandable, for all levels of literacy. It will be professionally translated into the languages most relevant to the study population and local site translation services will be used to aid discussions around the opt-out consent process for quantitative data collection as well as consenting for the parent survey and focus groups/ semi-structured interviews.

The risk of data breach will be minimised by entering pseudonymised data into an encrypted data collection tool (REDCap) with data held within QMUL with our data Safehaven. Data entered here will not be linked to any participant-identifiable information. Parent survey responses will also be held in the encrypted NHS Microsoft 365 Forms platform and no patient identifiable data will be collected. Parent focus group/ semi-structured interview transcripts will be securely stored and only accessible to study teams for thematic analysis.

If the study enrolment happens as planned, there should be no delay in receipt of standard of care. However, should there be a misunderstanding between the midwifery and medical staff, there is a very small risk routine care would be delayed. This will therefore be highlighted very clearly in study team training to minimise this risk and ensure any clinical need is prioritised over study enrolment.

There is a risk that given the unblinded nature of the study, health care professional (HCP) perception of need for jaundice testing would be affected. We do not anticipate the number of jaundice tests at each site to increase due to participation in the study. However, we appreciate that the presence of an ongoing study may change healthcare worker behaviour, to minimise this the full details of the study will only be discussed with local study leads, who will not be the healthcare workers identifying patients for investigation for jaundice on data collection days.

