#### **Data Collection Methods**

#### 1. Quantitative data collection

Data will be collected on predetermined days on the postnatal areas of each participating site. Suitable days will be identified by the local lead at each site to fit with availability of study team members. Data will be collected by trained members of our research team from parents of participants, clinical records and healthcare professionals including nursery nurses and midwives.

The following data will be collected:

Table 1: All datapoints collected for Primary Objectives 1 and 2

Datapoint	Source	Collection timepoint
Demographic details and baseline	data	
Eligibility confirmation	Medical record and/or direct questioning of parent/carer	Enrollment
Date of birth (dd/mm/yyyy)	Medical record	Enrollment
Time of birth (hh:mm)	Medical record	Enrollment
Gestational age (weeks + days)	Medical record	Enrollment
Birthweight (g)	Medical record	Enrollment
Ethnicity of birthing parent (recorded)	Medical record	Enrollment
Ethnicity of birthing parent (reported)	Direct questioning of parent/carer	Enrollment
Ethnicity of 2nd biological parent (if known)	Direct questioning of parent/carer	Enrollment
Index of Multiple Deprivation (as calculated by postcode of birthing	Medical record	Enrollment

		1
parent)		
Need for translator	Direct questioning of parent/carer	Enrollment
Jaundice and skin tone assessmen	t	
Feeding method a	Direct questioning of parent/carer	Enrollment
Skin tone as per skin tone tool b	Skintone assessment by study team member	Enrollment
Indication for jaundice assessment c	Medical record and/or HCP that identified eligible participant	Enrollment
TcB measurement d	Medical record and/or HCP that identified eligible participant	Enrollment
Serum bilirubine	Medical record and/or HCP that identified eligible participant	Enrollment
Immediate management planf	Medical record	Enrollment
Retrospective		
Duration of admission	Medical record	14 days
Location of admission	Medical record	14 days
Treatment administered 	Medical record	14 days
Feeding at discharge a	Medical record	14 days
Investigation results h	Medical record	14 days
Has the participant been diagnosed with G6PD deficiency and/or haemolytic disease of the newborn (HDN)	Medical record	14 days

<sup>a Exclusively breastfeeding, Mixed feeding, Exclusively formula feeding

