# 9. Study procedures

#### **Opt-out Consent (Primary Objectives and Secondary Objective 1):**

- An opt-out consent model will be used for the primary objectives. This means that all eligible participants will be enrolled unless either of the parents / carers actively opt out. However, agreement from one parent is sufficient if the second parent is not present.
- A verbal and written explanation of the study will be provided, explaining the study objectives, procedures, risks, and benefits alongside the opt-out consent model.
- The written information will be available in a range of languages appropriate to the local population for each site.
- If required, a professional translator will be used to translate all relevant information, either in person or telephonically.
- Parents will be given a minimum of 15 minutes to consider the information and to ask questions as required, before study data is collected. The PIS will contain details on how to contact the study team to opt-out at any later stage.
- If parents opt-out of inclusion in the study, there will be no impact on the routine care provided

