## **Screening and recruitment:**

- On data collection days, staff members carrying out jaundice assessments in relevant inpatient areas will be notified and asked to alert the research team when any neonates are undergoing their first TCB or SBR
- Standard clinical care will not be delayed for enrollment
- Identification of potential eligible babies will occur via a written identification table in postnatal areas. Outcomes, i.e. included or excluded, and reasons for exclusion will be noted in the infant's clinical record.
- The research team at each site will consist of the local lead and a number of additional data collectors who have undergone training. These individuals will review whether or not these neonates meet the eligibility criteria, and approach the birthing parent to discuss the study if eligible
- Study data will be collected in participants where all eligibility criteria are met

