#### Skin Tone Tool & Language Use

- Discussion around skin tone tool not covering all possible skin tones, worth highlighting we are categorising by closest match and conveying this clearly in PIS and conversation
- Some parents were uncertain about their baby's "natural" skin tone due to jaundice, suggested perhaps "expected skin tone". "Healthy skin tone" not a good alternative due to the connotation of baby being unhealthy.
- Parents agreed that the study team should assign skin tone categories for consistency, but consider how to address situation if parents disagree
- All parents found the language used acceptable and appropriately sensitive

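### The skin tone grade is subjective, normally follows the first bilirubin test, and is not protected from knowledge of the result

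*Protocol*

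**What the plan says.** All references are to the protocol.

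- **Timing.** Section 8 (Study processes during prospective data collection phase): "Neonates will undergo a visual inspection by local study team members within twelve hours of their first bilirubin measurement". Section 9 (Screening and recruitment) has ward staff "asked to alert the research team when any neonates are undergoing their first TCB or SBR", and section 9 (Opt-out Consent) adds "Parents will be given a minimum of 15 minutes to consider the information" before any study data are taken.
- **Who grades.** Table 1 gives the source of the grade as "Skintone assessment by study team member", at enrolment. Section 8 describes the team as "all of whom are paediatric resident doctors as part of the direct care team".
- **Where the outcome comes from.** Table 1 gives the source of both TcB and SBR as "Medical record and/or HCP that identified eligible participant", also at enrolment. Indication, management plan and parental ethnicity share that timepoint, and no order is stated.
- **What is timed.** The footnotes to Table 1 ask for date and time of TcB and of SBR. They list no time of grading.
- **Safeguards.** The protocol has tool training aimed at sensitive language and agreement between users, assignment to the group nearest the natural colour, and a well-lit room. The one observer effect it discusses (sections 5.3 and 11) is on the decision to test.
- **Parent feedback.** In the focus group summary (Skin Tone Tool & Language Use), some parents were unsure of their baby's natural "skin tone due to jaundice".
- **Analysis.** Section 10.2 compares tones 2, 3 and 4 with the baseline tone in a mixed model that includes age at measurement.

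**The concern.** In Objective 1 the grade is the explanatory variable and bilirubin is the outcome. If either the bilirubin value or its visible effect on the skin can move the grade, the exposure error depends on the outcome. Such error does not simply dilute the contrasts, as random misgrading would. It can create a tone gradient where none exists, or hide a real one.

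The question the study asks is whether darker-skinned infants are first tested at a higher bilirubin. The expected answer is easy to guess, and the local leads, who belong to the grading team, know the study in full. A doctor choosing between two adjacent categories, with the value and the parents' ethnicity at hand, has room to drift without intending to.

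The protocol treats altered skin colour as a threat to grading when it excludes conditions that cause it (section 7.2). Jaundice alters colour too and cannot be excluded. Without the time of grading, or a note of whether the value was known, nobody can examine the problem afterwards.

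**Working it through.** **1. Order of events.** The team is alerted when the first test is being done. It then checks eligibility, explains the study and waits at least 15 minutes. Grading is part of the study data, so it normally follows the test. The twelve-hour window leaves time for a result, and possibly for treatment, to come first. TcB and SBR may be obtained from the member of staff who flagged the infant, so the value can be known before the infant is undressed. The protocol contains no masking step, no required order and no time field for the grade.

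**2. Size, as an illustration.** The protocol gives no misgrading rate, so there is no stated figure to reproduce.

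Inputs from section 10.1: tone shares 0.5, 0.2, 0.2, 0.1; age uniform over 0–96 hours; slope 2.6 per hour; residual SD s = 10; target of 10 µmol/L for tone 2 versus 1.

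Assumptions: no true tone effect; misgrading probability q = 0.1 or 0.2; a second value s = 40. The earlier study quoted under Primary Objective 2 has SDs of 34–43, but those are not age-adjusted residuals.

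*Rule A: bilirubin high for age.* Infants with a positive age-adjusted residual are graded one step darker with probability q (tone 4 stays). Let c be the mean of the positive part of the residual, c = s/√(2π) = 0.399s.

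- Graded tone 1: mean residual −qc/(1 − q/2)
- Graded tone 2: mean residual 0.3qc / [0.2(1 − q/2) + 0.25q]
- Graded tone 3: mean residual 0
- Graded tone 4: mean residual 0.2qc / (0.1 + 0.1q)

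For s = 10 and q = 0.1, c = 3.99. Tone 1: −0.399/0.95 = −0.42. Tone 2: 0.1197/0.215 = 0.56. The false difference is 0.56 + 0.42 = 0.98.

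*Rule B: absolute bilirubin above the median.* The age term 2.6 × (age − 48) is uniform over ±124.8, so an infant with residual e is above the median with probability of about 0.5 + e/249.6. The same formulas then hold approximately with c = s²/249.6, which is 0.40 at s = 10 and 6.41 at s = 40. Age adjustment removes the rest.

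*Rule C: as A, but one step lighter.* Tone 2 versus 1 becomes −0.2qc/(0.5 + 0.1q). For s = 40 and q = 0.1, c = 15.96 and the difference is −0.319/0.51 = −0.63.

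False differences for tones 2 / 3 / 4 versus 1 (µmol/L):

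| Rule | q | SD 10 | SD 40 |
|---|---|---|---|
| A | 0.1 | 1.0 / 0.4 / 1.1 | 3.9 / 1.7 / 4.6 |
| A | 0.2 | 1.9 / 0.9 / 2.2 | 7.7 / 3.5 / 8.9 |
| B | 0.1 | 0.1 / 0.0 / 0.1 | 1.6 / 0.7 / 1.8 |
| B | 0.2 | 0.2 / 0.1 / 0.2 | 3.1 / 1.4 / 3.6 |
| C | 0.1 | −0.2 / −0.4 / −0.6 | −0.6 / −1.4 / −2.3 |
| C | 0.2 | −0.3 / −0.7 / −1.2 | −1.2 / −2.9 / −4.8 |

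A large simulation of the age-adjusted model gave the same values within simulation error.

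**3. False positives.** I simulated 560 infants in 20 hospitals (hospital as fixed effects, assumed hospital SD 5), with a joint 5% test of the three contrasts. Under rule A the rejection rate was 10–13% at q = 0.1 and 37–41% at q = 0.2, for residual SDs of 10 to 43. Under rule B it was 5–8%. With accurate grading it was 4–5%.

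**The case against.** The protocol is not careless about the grade. It uses a scale it describes as the only published validated one for neonates, trains the users, undresses the infant in good light and asks for the natural colour. Parents agreed that the team should assign the category for consistency. These steps limit drift, but none of them is masking. Nor can masking be complete, since a direct-care doctor may already know the value.

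Several stronger readings are tempting, and the documents do not support them:

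- **That the bias runs away from the null.** Nothing says jaundiced infants are graded darker. If they are graded lighter, a true disparity shrinks.
- **That every infant is jaundiced when graded.** Infants tested because of risk factors, routinely or incidentally are also enrolled. The colour route affects part of the sample, while knowledge of the result can affect all of it.
- **That one doctor collects everything, or that grading always comes after the test.** The protocol describes a team and says within twelve hours of the measurement. That grading comes afterwards is the usual case, inferred from the process.
- **That the protocol calls the graders unblinded.** The phrase "given the unblinded nature of the study" in section 5.3 concerns the perceived need for testing. The absence of masking for graders follows from silence and from the shared data collection.
- **That absolute-bilirubin misgrading produces the larger figures.** It does so only if age is left out of the model, and section 10.2 includes it.
- **That Objective 2 is biased as well.** It analyses paired TcB–SBR differences. Regrading by bilirubin level matters there only if the difference varies with level, which has not been shown.

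**Conclusion.** The gap is real and is a matter of study conduct: a subjective exposure grade, normally made after the outcome is measured, by staff with access to it, with no masking, order or timing record. An analysis plan cannot supply this later, because the needed facts would never have been recorded.

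The size is uncertain. At the protocol's SD of 10, the false tone 2 versus 1 difference is at most about 2 µmol/L in the scenarios above. It reaches about 4–8, close to the target of 10, only if graders respond to bilirubin high for age, 10–20% of those infants are moved one step darker, and the residual SD is about 40. Misgrading on absolute bilirubin gives about 0.1–0.2 at SD 10 and 1.5–3 at SD 40. Grading lighter gives negative differences. The misgrading rates, the rules and SD 40 are all assumptions. The case for acting rests on the low cost of prevention and on the impossibility of checking afterwards, not on a demonstrated bias.

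**What to change.** 1. In sections 8 and 9, require the tone grade to be assigned and locked in REDCap before the data collector opens the bilirubin value, management plan or parental ethnicity, wherever the value is not already known. Eligibility needs only the fact that a first test is being done.
2. Add three fields to Table 1 and the CRF: time of grading, whether the grader knew the result, and whether phototherapy had started at grading.
3. Pre-specify a sensitivity analysis of Objective 1 limited to infants graded without knowledge of the value and before phototherapy.
4. Add a line to the tool training explaining why the grade comes first.

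The cost is a change of CRF page order, three fields and a training point. It needs no extra staff or visits and does not alter care, but it must be in place before data collection. The drawback is that some direct-care graders will already know the value and must record that, so the sensitivity analysis will rest on a smaller sample.
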